7.2.2 Safety Endpoints

7.2.2.1 Secondary Safety Endpoints

- Incidence of treatment-emergent adverse events (TEAEs) related to BBL.
- Incidence of treatment-emergent serious adverse events (TESAEs) related to BBL.

8 CLINICAL INVESTIGATION PLAN

8.1 Overview of Study Design

This is a prospective, multicenter, randomized, comparative, evaluator-blinded pivotal study designed to evaluate the safety and effectiveness of BBL for the correction of volume loss in the IOH. Study subjects will have a screening period of up to 10 days and participate for a maximum duration of 76 weeks (\pm 14 days).

A total of 150 subjects will be randomized at up to 9 investigational sites in the United States (US). At each study site, the number of subjects randomized should not exceed 26. A minimum of 20% of enrolled subjects will be Fitzpatrick Skin Type IV, V, or VI Subjects from the Fitzpatrick Skin Type IV, V, or VI group will be distributed as follows: at least 16 subjects of Type IV; 7 subjects of Type V; and 7 subjects of Type VI. At least 10% of the subjects enrolled will be male.

Subjects eligible for study enrollment will have symmetrical right and left IOHs with the same MIHAS score of 2 or 3 (moderate or severe), as assessed live by a blinded evaluator. All blinded evaluators will be qualified healthcare practitioners, delegated by the treating investigator and trained by the sponsor. At screening, eligible subjects will be randomized to 4 groups using a 2:2:1:1 ratio as follows: BBL with needle (TN), BBL with cannula (TC), control/delayed-treatment BBL with needle (CDTN), and control/delayed-treatment BBL with cannula (CDTC). The needle or cannula assignment for a subject cannot be interchanged during the study; that is, needle and cannula cannot be used in the same subject.

Subjects randomized to treatment will receive a BBL injection in both IOHs at Day 1. Treated subjects who do not achieve optimal aesthetic correction or at least 1-point improvement on the MIHAS, as assessed by the blinded evaluator 4 weeks post treatment compared to baseline, may have a touch-up injection in one or both IOH(s). If a touch-up is necessary, it will only be administered if there are no medical contraindications or existing AEs of concern, as determined by the treating investigator. The treating investigator will be responsible for reviewing whether the threshold for optimal aesthetic correction or at least 1-point MIHAS improvement is met, as assessed by the blinded evaluator, since the blinded evaluator will not have access to the subject's study records.

Subjects who achieve at least 1-point improvement on the MIHAS 4 weeks post treatment when compared to baseline may have a touch-up injection in one or both IOH(s) to achieve optimal correction, at the discretion of the treating investigator and the subject.

Subjects randomized to treatment at Day 1 will have the option for retreatment, upon agreement between the subject and the treating investigator, at 48 weeks post last injection

(i.e., baseline injection or touch-up, if applicable) and will then be followed for an additional 24 weeks, for a total study duration of up to 76 weeks (72 weeks if no touch-up is performed).

Subjects randomized to the control/delayed-treatment group will remain untreated until Week 8. After all applicable effectiveness endpoint assessments have been completed at their Week 8 visit, control subjects will receive BBL IOH injections (i.e., delayed treatment) and will be followed for 48 weeks. Subjects who do not achieve optimal aesthetic correction or at least 1-point improvement on the MIHAS as assessed by the blinded evaluator 4 weeks post treatment compared to the delayed-treatment baseline (Week 8), may have a touch-up injection in one or both IOH(s). If a touch-up is necessary, it will only be administered if there are no medical contraindications or existing AEs of concern, as determined by the treating investigator. The treating investigator will be responsible for reviewing whether the threshold for optimal aesthetic correction or at least 1-point MIHAS improvement is met, as assessed by the blinded evaluator, since the blinded evaluator will not have access to the subject's study records.

Subjects who achieve at least 1-point improvement on the MIHAS 4 weeks post treatment when compared to the delayed-treatment baseline (Week 8) may have a touch-up injection in one or both IOH(s) to achieve optimal correction, at the discretion of the treating investigator and the subject.

Control/delayed-treatment subjects will not be offered retreatment.

Any time a subject is treated (i.e., initial injection, touch-up, and/or retreatment), he/she will have a 72-hour post-treatment phone call to evaluate safety. If a subject reports a safety concern during any phone call, an unscheduled visit may be necessary.

Effectiveness assessments include blinded evaluator MIHAS, treating investigator and subject GAIS, subject-reported FACE-Q Satisfaction with Eyes, FACE-Q Appraisal of Lower Eyelids, FACE-Q Patient-Perceived Age VAS, a Patient-Perceived Pain VAS, and a likelihood of future treatment assessment. These assessments will be performed throughout the study. Additionally, three blinded, board-certified IPR experts who are not part of the study sites will assess subject IOHs using the MIHAS and subject photographs.

Standard safety parameters will be monitored throughout the study. Additionally, visual assessments (i.e., visual acuity, confrontation visual field test, ocular motility, and an undilated central retinal exam using non-mydriatic retinal cameras and read by a central reader) will be conducted. A subject eDiary will be used to record predefined CTRs for 28 days after the initial injection, touch-up injections (if applicable), and retreatment (if applicable).

CCI

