Version 5.0, 04- NOV-2021	An incorrect instruction in footnote 6 in the schedule of events for the control/delayed-treatment subjects was included in previous versions of this protocol. The footnote incorrectly stated that IOH photos should only be taken at Visit C1-a (8 weeks after screening), if the screening photos were deemed unsatisfactory. In fact, all subjects in the control/delayed-treatment group should have IOH photos taken at Screening and Visit C1-a, as outlined in other sections of the protocol. The issue was noted after all control/delayed-treatment subjects had completed the affected Visit C1-a and for the majority of control/delayed-treatment subjects, no photo had been taken at Visit C1-a. The following changes to the planned IPR assessments, and statistical analyses were therefore included in this protocol amendment: • Updated timepoints of photos used for IPR assessment in Section 7.2.1.3 Other Effectiveness Endpoints and Section 11.2.1.1 Merz Infraorbital Hollow Assessment Scale (MIHAS). For subjects in the control/delayed treatment group, photos from Screening, 8 weeks post-screening and 8 weeks post last injection will be included in the IPR assessment. • Adapted the analyses of IPR assessment data to the change in timepoints of photos used in the assessment. For subjects in the control/delayed-treatment group, summaries will be provided for 8 weeks after screening and 8 weeks post-last injection, using the screening photo as reference. • Reference to pre-treatment photos taken at the delayed treatment baseline were removed from the definition and analysis descriptions for the GAIS endpoints. In Section 11.1 Visit Schedule, the definition of the primary endpoint visit, which is 8 weeks post screening for the control/delayed treatment subjects, was corrected. Minor formatting errors and wording changes were implemented.
Version 4.0, 27- JAN-2021	 Updated safety email address and removal of fax number (Section 12.2.2) Increased the maximum enrollment per site from 24 to 26 (Sections 8.1, 9.1, 13.1) Updated internal functional contributors (Section 16.5)
Version 3.0, 20- JUL-2020	In order to address the agency's (FDA) concerns regarding changes in visual function assessments that may occur immediately after treatment,

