11 STUDY PROCEDURES

11.1 Visit Schedule

CCI

To determine subject eligibility for study participation, a screening evaluation must be completed from -10 to -3 days before baseline. Eligible subjects will be randomized at the screening visit.

After screening evaluation, each subject randomized to treatment will have between 10 and 14 visits, depending on whether he/she receives a touch-up and/or retreatment injection.

Subjects randomized to control will remain untreated until Week 8, when the primary effectiveness endpoint is evaluated. Upon completion of all effectiveness assessments, control subjects will be treated with BBL (i.e., will receive delayed treatment). After screening evaluation, each subject in the control/delayed-treatment group will have between 8 and 10 visits, depending on whether he/she receives a touch-up injection.

The primary endpoint visit will occur at Week 8 (+7 days) post last injection (i.e., initial injection or touch-up, if applicable) for the treatment group and at Week 8 (+7 days) after screening for the control/delayed-treatment group.

For subjects in the treatment group, the final visit will occur 72 weeks (± 14 days) post last injection (initial or touch-up, if applicable) or 24 weeks post retreatment (if applicable).

For subjects in the control/delayed-treatment, the final visit will occur 48 weeks (\pm 14 days) post last injection (initial or touch-up, if applicable).

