During the baseline and subsequent study visits, subjects will be evaluated live on the MIHAS by a trained evaluator (i.e., a qualified healthcare practitioner delegated by the treating investigator); this evaluator is blinded to the subject's treatment assignment and will perform the respective assessment independently from any study staff. Prior to study enrollment, at least one blinded evaluator at each site will be trained and qualified by the study sponsor to perform scale-grading assessments. Training will consist of an instructional session, followed by a qualification where blinded-evaluator trainees will score two sets of photographs, representing a variety of different MIHAS grades, at least two weeks apart. The purpose of this assessment is to obtain intra- and inter-evaluator reliability qualification analyses prior to starting the study at their respective site (i.e., weighted Kappa/ICC analyses). Any blinded evaluator who does not successfully achieve an intra- and inter-rater (pair-wise against other raters) reliability point estimate value of ≥ 0.70 will be retrained and requalified up to two times. If evaluator retention (e.g., change in personnel) becomes an issue during the study, new blinded evaluators must be trained by the sponsor, and respective qualification analyses must be performed. Qualification and training of blinded evaluators will be documented. At each study site, all efforts should be made to plan for and maintain the same blinded evaluator for all assessments throughout the study. To account for illness or unplanned absence of the blinded evaluator, it is recommended to have at least one back-up blinded evaluator trained and qualified per site. Evaluators will be re-trained on the MIHAS at regular intervals (approximately every 3 months at a minimum).

The treating investigator will also attend a MIHAS-instructional session to ensure understanding of the subject-eligibility criteria of right and left IOH volume deficit with a rating of 2 or 3 (moderate or severe) at study entry.

Additionally, three blinded IPRs will assess subject photographs using the MIHAS.

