Note: For subjects randomized to treatment, the photographs assessed will be from Screening or Day 1 (Visit V1a) **and** 8 weeks post last injection (Visit V3). For subjects randomized to the control/delayed-treatment group, the photographs assessed will be from Screening, Day 1 (8 weeks from the screening visit, Visit C1a) and 8 weeks post last injection (Visit C3).

These board-certified IPRs, who are not part of the study sites, will be qualified using the methodology described for blinded evaluators above. Further details regarding photographs are provided in Section 11.2.1.2.

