SAS PROC MI will be used to create 100 sets with imputed MIHAS scores per treatment group (TRT and CTL) and per IOH (left and right). For each treatment group and IOH, a different seed will be used for implementation. For treatment group TRT, a seed of 2793 and a seed of 8210 will be used for left and right IOH, respectively. Regarding the control group CTL, a seed of 3913 and a seed of 7956 will be used for left and right IOH, respectively. Baseline MIHAS, Week 4 (Visit 2-a) MIHAS, (pooled) site, and touch-up (yes/no) will be included in the multiple-imputation model for subjects in the TRT group. Details on pooling of sites are described in Section 6.4.5. If Week 4 MIHAS scores are missing, then these will be imputed using the same covariables available up to the respective time point, before imputing Week 8 MIHAS scores. Baseline MIHAS and (pooled) site will be included in the multiple-imputation model for subjects in the CTL group. The default number of burn-in iterations before each imputation (20) will be used for all imputation models. In order to ensure reproducibility, the data will be sorted by subject identifier (USUBJID) prior to imputation. SAS code similar to the following will be used:

Subsequently, it will be determined for each subject within each of the imputed datasets, whether response is achieved at Week 8 $(\ge 1$ -point improvement from baseline on MIHAS of both IOHs).

This code assumes that 'response' is coded with '1' and 'no response' is coded with '0'. Moreover,

This code assumes that 'response' is coded with '1' and 'no response' is coded with '0'. Moreover, midata_8w_trt_left, midata_8w_trt_right, midata_8w_ctl_left and midata_8w_ctl_right are the subsets of midata_trt_left, midata_trt_right, midata_ctl_left and midata_ctl_left, respectively, and will include only the MIHAS scores at baseline and at Week 8.

For the Hypothesis Test 1, the Wilson CI for the response rate in the TRT group ($[WL_{TRT}, WU_{TRT}]$) will be calculated using the following steps, as detailed in [1]:

1. The mean sample response \hat{p}_{Imp} and sample variance $\widehat{U}_{Imp},$

$$\widehat{U}_{Imp} = \frac{\widehat{p}_{Imp} (1 - \widehat{p}_{Imp})}{n},$$

will be calculated for each of the m=100 imputed datasets with sample size n.

2. The overall mean \bar{p}_m and variance \bar{U}_m over all imputed datasets will be calculated:

$$\bar{p}_m = \frac{1}{m} \sum_{lmp=1}^m \hat{p}_{lmp},$$

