The time in weeks from randomization until premature discontinuation from study up to Week 8 will be displayed using a Kaplan-Meier curve. This curve will be provided for subjects in TRT and CTL groups based on all subjects randomized. Subjects who do not discontinue the study within the specified time window will be presented as censored at the date of their Week 8 visit. Subjects in TRT group that missed their Week 8 visit but did not discontinue will be censored at the target day of the Week 8 visit (i.e. Day 57 after last injection in treatment Cycle 1). For subjects who attended only visits up to Week 8 with date of last contact after Week 8, the date of discontinuation will be set to the date of the Week 8 visit.

The time in months from first treatment until premature discontinuation from study will be described by a second Kaplan-Meier curve for the TRT and DTRT groups in SP. Subjects who complete the study will be presented as censored at end of study.

Visit attendance (subjects expected at visit, subjects with visit performed on-site, subjects with visit performed virtually, subjects with missed visit due to COVID-19 pandemic or other reasons, subjects discontinued) will be presented in a frequency table for various treatment groups (i.e., TN, TC, TRT, CDTN, CDTC, CDTRT) based on all randomized subjects.

For 'Study discontinued', the cumulative number of subjects who discontinued the study before the respective visit will be displayed. For 'Subjects expected at visit', the following visits are defined as expected for all randomized subjects: Screening visit, initial treatment visit V1-a, V1-b, V2-a, V3 – V7-a, V8, V9 for TRT subjects; and Screening visit, visits C1-a, C1-b, C2-a, C3 and all following visits for CDTRT subjects, as defined in the visit schedules in the CSP column for TRT subjects and column for CDTRT subjects). Visits V2-b/C2-b and V2-c/C2-c are

only expected for subjects receiving an optional touch-up at visit V2-a/C2-a. In case of retreatment at visit V7-a for TRT subjects, follow-up visits V7-b and V7-c are also expected. For subjects who discontinue the study, the end of study visit V9/C7 is expected. Visits after premature discontinuation are generally not expected. The number of 'Subjects expected at visit' is thus calculated as number of randomized subjects – the number of subjects discontinued before the respective visit.

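### Does the treated arm's extra Week 4 grading undo the evaluator's blind at the primary assessment?

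*Protocol*

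**What the plan says.** **Treated subjects.** Protocol Section 8.1 has the evaluator grade them four weeks after injection; those short of the threshold, "as assessed by the blinded evaluator 4 weeks post treatment compared to baseline, may have a touch-up injection in one or both IOH(s"). SAP Section 6.1.1.1 confirms that this score exists in the treated arm: "Baseline MIHAS, Week 4 (Visit 2-a) MIHAS, (pooled) site, and touch-up (yes/no) will be included in the multiple-imputation model" for that group. The primary grading follows at Visit 3, eight weeks after the last injection.

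**Controls.** The visits the SAP expects (under Disposition of subjects) are "Screening visit, visits C1-a, C1-b, C2-a, C3 and all following visits for CDTRT subjects". C1-a is the primary grading and comes directly after Screening. The control imputation model accordingly has no Week 4 term: "Baseline MIHAS and (pooled) site will be included in the multiple-imputation model for subjects in the CTL group".

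**Timing.** Protocol Section 11.1 sets the primary visit at Week 8 (+7 days) after the last injection "for the treatment group and at Week 8 (+7 days) after screening for the control/delayed-treatment group".

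**Evaluator.** Protocol Section 11.2.1.1 says: "At each study site, all efforts should be made to plan for and maintain the same blinded evaluator for all assessments throughout the study". The evaluator has no access to study records (Section 8.1) and grades independently of study staff (Section 11.2.1.1).

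**Photo panel.** Three off-site blinded raters also grade photographs. For treated subjects "the photographs assessed will be from Screening or Day 1 (Visit V1a"), together with those from eight weeks after the last injection. The version 5.0 amendment summary reports that most controls have no C1-a photograph, and adds: "The issue was noted after all control/delayed-treatment subjects had completed the affected Visit C1-a".

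**The concern.** The primary endpoint is a subjective live grade, the comparator is no treatment, and no sham is described, so the evaluator's blind is the main protection against biased grading. On the scheduled visits, anyone graded between Screening and the primary visit has been treated. An evaluator who recalls such a grading at Visit 3, or knows roughly how long ago the subject was screened, has a clue to allocation. Lack of access to records and separation from staff remove neither memory nor a sense of elapsed time.

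If that clue led to generous grading of treated subjects, it would raise both the treated response rate tested against 50% (Step 1) and the difference from control (Step 2). Step 1 is the more exposed: it sets one arm against a fixed value, so randomisation gives it no protection. The visible SAP text neither mentions the asymmetry nor offers a check; Section 6.1.1.4 contains only summaries of the scores.

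**Working it through.** **1. Is the asymmetry real?** Count the SAP's expected visits after Screening.
- Treated: V1-a, V1-b, V2-a, V3, V4, V5, V6, V7-a, V8, V9 = 10; with V2-b, V2-c, V7-b, V7-c = 14.
- Control: C1-a, C1-b, C2-a, C3, C4, C5, C6, C7 = 8; with C2-b, C2-c = 10.

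Protocol Section 11.1 gives 10 to 14 and 8 to 10. The counts agree, leaving no room for a control visit before C1-a.

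**2. How clear is the timing clue?** Screening is 3 to 10 days before Day 1. Days from screening, using the windows as printed:

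| Primary visit | Calculation | Days |
|---|---|---|
| C1-a | 56 to 56+7 | 56–63 |
| V3, no touch-up | 3+56 to 10+56+7 | 59–73 |
| V3, touch-up at its nominal day | 3+28+56 to 10+28+56+7 | 87–101 |

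If the printed +7 stands for ±7 (Protocol Section 11.3 speaks of ±7-day windows), the ranges become 49–63, 52–73 and 80–101. Only touch-up subjects separate cleanly from controls.

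**3. The plan's own figures.** Step 1, exact binomial with n=80 and rejection at 50 or more responders: power 94.1% (stated at least 94%). Step 2, one-sided Fisher test, 80 versus 40 at 70% versus 30%: 98.4% (stated at least 98%). Product 92.6% (stated above 92%). 120/(1−0.20) = 150. All reproduce, and none depends on the visit pattern.

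**4. What would drift do?** Assume a share d of true treated non-responders is graded as responders, so p₁ = p + d(1−p). Take complete data with n = 100 and 50, and enumerate both binomials. Step 1 passes if the Wilson lower limit exceeds 50% (60 or more of 100); Step 2 passes if the Newcombe lower limit exceeds 0. Probability of passing both:

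| True rates, treated vs control | d=0 | d=5% | d=10% |
|---|---|---|---|
| 30% vs 30% | about 0 | about 0 | about 0 |
| 50% vs 50% | 0.7% | 2.1% | 5.1% |
| 50% vs 30% | 2.8% | 7.9% | 18.1% |
| 60% vs 30% | 53.8% | 69.4% | 82.1% |
| 70% vs 30% (planned) | 98.6% | 99.4% | 99.8% |

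If the same share of control responders is also downgraded, the 50% vs 50% row becomes 3.0% and 9.8%.

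**5. Tipping counts.** With 70/100 versus 15/50, Step 1 fails once 11 treated responders are reclassified and Step 2 once 24 are. With 56/80 versus 12/40 the counts are 8 and 18.

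**6. Could the photo panel supply the check?** One might set the Step 1 count of 11 against the treated subjects who respond on the live grade but not on the panel's. That cell fills without any bias. With both response rates at 70% and agreement kappa, its expected size per 100 is 100 × 0.70 × 0.30 × (1−kappa) = 21(1−kappa). For assumed kappas of 0.7, 0.5 and 0.4 this gives 6.3, 10.5 and 12.6. Unbiased data could therefore reach 11.

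**The case for a change.** The strongest case for acting is that a foreseeable weakness in a pivotal study's main protection can be examined cheaply. Sites are capped at 26 subjects, so remembering a face is plausible. The treated Visit 3 photographs are already planned, and Protocol Section 13 leaves the SAP open until database close. A harsher drift model also gives larger numbers. With 80 and 40 subjects, a true rate of 50% in both arms, and drift of 5 or 10 percentage points upward in treated subjects and downward in controls, the chance of passing both steps rises from 0.6% to 7.6% or 35%.

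Much of this stands as description: the asymmetry exists, and Step 1 is sensitive near 50%. It does not carry the conclusion.

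- **The mechanism is conjecture.** The evaluator must remember the subject, know the arm-specific schedule, and then grade differently because of it. The documents show none of these. Visit count does not identify a control either: C1-a is a control's second grading, just as V2-a is a treated subject's. Downgrading controls therefore needs the timing clue, which overlaps with treated subjects who had no touch-up.
- **The drift figures do not isolate the Week 4 visit.** They would describe any upward grading bias. Without a sham, visible correction is itself a clue.
- **Absence cannot be asserted.** Protocol Section 10.4, the Schedule of Events, SAP Section 6.1.1.2 and the panel analysis are not in the public text. SAP Section 6.4.4 refers to subgroup analyses of panel endpoints, so a panel summary exists and an added one might duplicate it.
- **The checks are weak.** Splitting results by same or different evaluator is not randomised, may leave one group almost empty, and requires rater identity to have been recorded. The panel cannot test Step 2, because most control C1-a photographs are missing.

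**Conclusion.** No change to the plan follows. The unequal visit pattern is a possible limitation of the evaluator's blind; it is neither demonstrated unblinding nor an error. It comes from a fair trade-off: the Week 4 grade serves the touch-up decision, and keeping one evaluator limits rater-to-rater noise in a change score. The control side could not be altered now in any case, since every control had passed C1-a by protocol version 5.0.

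On size, assumed drift of up to 10% of treated non-responders moves the planned-rate result from 98.6% to 99.8%. It makes a false claim more likely mainly where the true treated rate is close to 50%. The pilot rates cited in Protocol Section 13.2, above 80% observed and above 70% with missing data counted as non-response, point away from that region. These figures assume complete data, 100 and 50 subjects, and a drift that nothing in the documents measures.

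A sentence in the study report noting the asymmetry, and that the photo panel cannot check the control comparison, is ordinary good reporting. If live and panel response rates in the treated arm are shown side by side, both discordant cells should be given under a stated rule for combining the three raters. Neither step affects the confirmatory tests or requires a SAP amendment.
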